	3. Dose Modification Guidelines and Management for Rash				
	4. Pneumonitis Guidelines				
	5: Dose Escalation Decision Rule Summary				
	6. Infusion Reaction Treatment Guidelines				
	7. Guidelines for Supportive Care of Rash from Trametinib				
	8. Tissue Summary				
	9. Laboratory Tests				
	0. Evaluating Adverse Events				
r abie 2	1. Froduct Descriptions	. / 3			
	LIST OF FIGURES				
Figure	1. Response rates to pembrolizumab according to mutation status	14			
	2. In vivo antitumor activity in CT26 Mouse Model dependent on sequencing of MEK	. 17			
ı igui t	inhibition with trametinib and PD-1 blockade (Liu et al, Clinical Cancer Research 2015)	.14			

LIST OF ABBREVIATIONS

AE adverse event

AST aspartate aminotransferase
ALT alanine aminotransferase
BAL bronchoalveolar lavage

β-HCG3 β-human chorionic gonadotropin

BID twice daily

CBC complete blood count

CLIA Clinical Laboratory Improvement Amendments

CNS central nervous system CR complete response

CRF case report form (paper or electronic as appropriate for this study)

CSR central serous retinopathy
CT computed tomography
DKA diabetic ketoacidosis
DLT dose limiting toxicity
DMSO dimethyl sulfoxide
DNA deoxyribonucleic acid

DSMB UCDCC Data and Safety Monitoring Board

ECI events of clinical interest

ECOG Eastern Cooperative Oncology Group EGFR Epidermal growth factor receptor ERK extracellular signal-regulated kinase

EU European Union

FDA Food and Drug Administration

FDAAA Food and Drug Administration Amendments Act FDAMA Food and Drug Administration Modernization Act

FFPE formalin-fixed, paraffin-embedded

GCP Good Clinical Practice
HBsAg hepatitis B surface antigen

HCV Hepatitis C

H&E hematoxylin & eosin

HIV Human Immunodeficiency Virus

IB investigator's brochure

ICH International Conference on Harmonisation

IHC immunohistochemistry
INR international normalized ratio
IRB institutional review board

ITIM immunoreceptor tyrosine-based inhibition motif ITSM immunoreceptor tyrosine-based switch motif

IV intraveinous

LDH lactate dehydrogenase LLN lower limit of normal mAb monoclonal antibody

MEK mitogen-activated extracellular signal-regulated kinase

MK-3475 pembrolizumab

MTD maximum tolerated dose

NCI CTCAE National Cancer Institute Common Terminology for Adverse Events

NSAIDS nonsteroidal anti-inflammatory drugs

NSCLC non-small cell lung cancer

NYHA
New York Heart Association
OCR
Office of Clinical Research
ORR
overall response rate
OTC
over-the-counter
PI
principal investigator
PD
progressive disease

PD-1 Programmed cell Death protein 1
PD-L1 Programmed Death-Ligand 1
PFS progression-free survival

PK pharmacokinetic

PBMC peripheral blood mononuclear cell

Pt platinum

PT prothrombin time

PTT partial thromboplastin time
QTc QT interval on electrocardiogram

RNA ribonucleic acid

RECIST Response Evaluation Criteria In Solid Tumors

RP2D recommended phase II dose

RPED retinal pigment epithelial detachment

RPPA Reverse Phase Protein Assays

RVO retinal vein occlusion
SAE serious advese event
SPF sun protection factor

SRC Scientific Review Committee

SU2C Stand Up to Cancer T3 total thriiodothyronine

T4 free thyroxine

T1DM Type 1 diabetes mellitus
TB Bacillus tuberculosis

TIL tumor-infiltrating lymphocytes
TKI tyrosine kinase inhibitors
TSH thyroid stimulating hormone

UCD University of California, Davis; UC Davis UCDCC UC Davis Comprehensive Cancer Center

ULN upper limit of normal

1.0 TRIAL SUMMARY

Abbreviated Title	A Phase Ib Trial of Pembrolizumab and Trametinib Focused on Advanced KRAS mutant Non-Small Cell Lung Cancer	
Trial Phase	Ib	
Clinical Indication	Advanced Non-Small Cell Lung Cancer Harboring a KRAS mutation	
Trial Type	Phase Ib with Expansion Cohorts	
Route of administration	Pembrolizumab (MK-3475) (Intravenous) Trametinib (Oral)	
Trial Blinding	Unblinded Open-label	
Treatment Groups	Phase I dose escalation of combination Pembrolizumab and Trametinib with lead in trametinib (cohort A) or lead in pembrolizumab (cohort B) in advanced NSCLC patients to determine the MTD and expansion phase dose. At the MTD, there are two Expansion Cohorts in KRAS Mutant NSCLC as follows: Cohort A: Lead in intermittent Trametinib for 1 cycle (3 weeks)	
	followed by intermittent Trametinib and Pembrolizumab Cohort B: Lead in Pembrolizumab for 1 cycle (3 weeks) followed by intermittent Trametinib and Pembrolizumab	
Number of trial subjects	We estimate 42 evaluable patients total (9 in each dose escalation cohort and 24 patients total for the dose expansion cohorts. A minimum of 12 patients (i.e., only 6 in each dose escalation arm if trial is terminated early due to unacceptable toxicity) and a maximum of 62 patients (18 patients in each dose escalation cohort and 24 patients total for the dose expansion cohorts.)	
Estimated enrollment period	2 years	
Estimated duration of trial	3 years	
Duration of Participation	3 years	

[figure not shown]
2.0 TRIAL DESIGN

2.1 Trial Design

This is a trial for patients with advanced or metastatic non-small cell lung cancer patients with KRAS mutations who have progressed on prior platinum-based frontline therapy. After the initial dose escalation with two different sequencing schemes (lead in trametinib and lead in pembrolizumab), in the expansion cohorts patients will be allocated to one of these two different arms: a) lead in trametinib followed by the intermittent trametinib/pembrolizumab and b) lead in pembrolizumab followed by intermittent pembrolizumab and trametinib to further define toxicities at the MTD, to determine the RP2D, to assess initial estimates of efficacy and to examine in the tumor and immune microenvironment changes in PD-L1 expression and T-cell subsets) across these two different sequencing schemes. Safety findings and preliminary efficacy will be employed as primary criteria for whether one or both treatment sequences may warrant further study. Exploratory immune correlates will be examined as secondary criteria to inform further development of this approach in future studies. The treatment arm that provides the better RR, PFS, safety profile and enhanced tumor immune microenvironment at rebiopsy will be recommended for further development. It is anticipated that $ORR \ge 50\%$ or a median PFS ≥ 8 months would be sufficient to recommend further development, provided safety and tolerability are acceptable. Patients will be treated until progression per RECIST 1.1 guidelines or intolerable toxicity.

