In several tumor types, in preclinical and translational studies the MEK-ERK pathway modulates PD-L1 expression, though different studies come to different conclusions regarding the degree and direction of this immunomodulation. In one preclinical study, PD-L1 expression is upregulated in melanoma cells resistant to BRAF inhibition and reversed by MEK inhibition with downregulation of PD-L1 and induction of apoptosis [4].

In a recently published clinical study, patient samples with metastatic melanoma BRAF inhibition increased PD-L1 expression while also enhancing markers of T-cell toxicity and providing a more favorable tumor immune microenvironment [5]. In other tumor types, studies suggest PD-L1 is also dependent on MEK/ERK and suppressed by MEK/ERK inhibition including Hodgkin's and Non-Hodgkin's Lymphoma and restores anti-immune activity [6].

Though there are somewhat discrepant conclusions regarding pre-clinical and clinical/translational data with MEKi and PD1/PDL1 inhibition in several tumor types, the weight of the evidence suggests that MEKi can potentiate the immune response and modulate PD-L1 expression. In KRAS mutant NSCLC treatment with selumetinib led to upregulation of PD-1 on CD8 T-cells and depletion of Treg with increase in PD-1 and CTLA-4 providing some rationale for integrating PD-1 blockade with MEK inhibition and highlighting the need to biopsy tissue on treatment to examine the tumor immune microenvironment[7]. Examination of immune correlates in tissue and blood in this early phase trial (including modulation of PD-L1 expression and T-cell subsets) are required to determine optimal sequencing of MEKi and PD1 antibody for maximum clinical impact.

This proposal builds a foundation for the study of pembrolizumab (MK-3475) with targeted therapeutic combinations incorporating MEK inhibitors in KRAS mutant NSCLC (a major unmet clinical need) and data regarding safety and tolerability from this proposal can be extended to other tumor types where MEK inhibition and PD1/PD-L1 blockade may be utilized.

Higher response rates with PD-1 blockade in tumors known to be highly mutated such as melanoma and NSCLC have been noted and we have observed higher responses in NSCLC

tumors with KRAS mutations (28% vs. 19%) suggesting potential roles for both KRAS and overall mutation burden in driving an adaptive immune escape phenotype (Figure 1).

Figure 1. Response rates to pembrolizumab according to mutation status

[figure not shown]

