All patients who receive a dose of pembrolizumab and trametinib will be analyzed for safety and efficacy. Subjects who discontinue from study participation prior to receiving the combination of trametinib and pembrolizumab will be replaced. Subjects in dose escalation who discontinue from study and are not evaluable for dose limiting toxicities will be replaced. Patients removed from study for unacceptable treatment related adverse event(s) will be followed until resolution or stabilization of all treatment related AEs to grade 2 or lower. However, they will not be replaced.

A group of 12 patients will be enrolled in each of the 2 expansion cohorts at the MTD. Patients will enroll into the next subsequent cohort upon completion of the previous cohort (Arm A then Arm B). A sequencing scheme will be considered as promising if at least 5 of 12 patients were to achieve a complete or partial response per RECIST 1.1. The decision rule is associated with 80% exact power with an exact alpha of 0.16 if the underlying response rate associated with a sequencing scheme were truly at least 50% compared to current expectation of 25% ORR with single agent pembrolizumab. A median PFS of 8 months in 12 patients per cohort will provide 81 power to detect a difference compared to historical PFS of about 4 months with single agent pembrolizumab with an alpha of 0.1 based on accrual time of 24 months and follow up of 12 months. A sequencing scheme will be recommended for further development based on a combination of promising efficacy (response rate, PFS) and favorable changes in the tumor immune microenvironment at rebiopsy, provided the safety and tolerability profiles are acceptable.

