All molecular and immune correlates will be assessed in exploratory analyses. Due to the limited sample size and exploratory framework, any such analysis will be stated carefully as hypothesisgenerating with the reported p-values not adjusted for multiple comparisons. Standard descriptive and graphical methods will be used to summarize the baseline levels and post-treatment changes for comparison of the three MEKi and pembrolizumab sequencing schemes, which will allow us to examine whether observed patterns are consistent with hypothesized mechanisms. The quantitative immune studies will be compared using a t-test to further inform the decision. Multiplicity of testing will not be considered since this considered an exploratory analysis. Association with response rate will be summarized descriptively by presenting the mean, SD, and other characteristics of molecular and immune measures, stratified by response status. Associations of molecular and immune measures with PFS will be summarized descriptively by stratified Kaplan-Meier curves and, if numbers permit, by proportional hazards models with molecular and immune responses as predictors. If the MEKi and pembrolizumab combination were not found to have sufficient activity, the molecular and immune patterns may

help explain the lack of activity. If sufficient activity were observed, then the correlates will be compared between patients who experience an objective response and those who did not. Results of these correlative studies including biopsies at pre-treatment and week 1 on treatment will be analyzed in conjunction with the Battle-Immunotherapy trial (with its later biopsy correlative timepoints) to inform the optimal dosing and sequencing of pembrolizumab with trametinib.

Decisions for whether to pursue one of these strategies in a larger trial will incorporate ORR, toxicity and immune correlative endpoints in collaboration with the company sponsors and SU2C Dream Team. The primary considerations will be ORR and toxicity, with immune and genomic correlative studies used as supplementary criteria.

If only one arm meets safety criteria and preliminary efficacy criteria (ORR \geq 50% or a median PFS \geq 8 months), then that treatment will be considered for future study. Immune and genomic correlative studies will be examined for the potential to inform future study design for that arm.

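### One sentence in Section 8.0 can be read as requiring a favourable immune change before a sequence is recommended, while Section 2.1 and later text in Section 8.0 set no such condition

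*Combined protocol and SAP*

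**What the plan says.** The immune data are given different roles in different places.

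- **Section 8.0, expansion-cohort paragraph.** Each arm enrols 12 patients. A sequence is called promising at 5 or more responses, with 80% exact power and an exact alpha of 0.16 for a true ORR of 50% against 25%. The paragraph ends by saying that a sequence will be recommended "based on a combination of promising efficacy (response rate, PFS) and favorable changes in the tumor immune microenvironment at rebiopsy", provided safety and tolerability hold up.
- **Section 2.1, four consecutive statements.** First: "Safety findings and preliminary efficacy will be employed as primary criteria for whether one or both treatment sequences may warrant further study". Second: "Exploratory immune correlates will be examined as secondary criteria to inform further development of this approach in future studies". Third: "The treatment arm that provides the better RR, PFS, safety profile and enhanced tumor immune microenvironment at rebiopsy will be recommended for further development". Fourth, an ORR of at least 50% or a median PFS of at least 8 months "would be sufficient to recommend further development, provided safety and tolerability are acceptable".
- **Section 8.0, decision paragraphs.** ORR and toxicity come first, "with immune and genomic correlative studies used as supplementary criteria". If one arm passes on safety plus ORR of at least 50% or median PFS of at least 8 months, it is considered for further study, and the correlates only inform the design of that study. If both pass with comparable results, covariate-adjusted models and then immune comparisons help choose between them. The final decision is left to clinical judgement.

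Neither section defines an enhanced or favourable microenvironment. On PD-L1, Section 4.3.1 reports that "different studies come to different conclusions regarding the degree and direction of this immunomodulation".

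**The concern.** The same expansion data can lead to different recommendations, depending on which sentence is applied. The trial is open-label, the arms have 12 patients each and the immune criterion has no threshold or direction. The choice of sentence could therefore be made after the results are known.

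Two things add weight. The on-treatment biopsy is taken in cycle 1, when, on the schedule in Section 5.2, only one of the two drugs has been given. And the power and alpha stand in the same paragraph as the recommendation sentence, so a reader may take them as properties of the recommendation.

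**Working it through.** **1. The plan's own figures.** Inputs from Section 8.0: n = 12, at least 5 responses, true ORR 0.50 against 0.25. With X binomial(12, p):

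- P(X ≥ 5 | 0.50) = 1 − (1 + 12 + 66 + 220 + 495)/4096 = 3302/4096 = 0.806
- P(X ≥ 5 | 0.25) = 0.158

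These match the stated 80% and 0.16. Section 8.0 attaches them to the label promising, not to the recommendation.

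**2. The other ORR criterion.** Section 2.1 and the decision paragraphs of Section 8.0 use an ORR of at least 50%. Read as an observed proportion, that is 6/12, because 5/12 = 41.7%.

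- P(X ≥ 6 | 0.50) = (3302 − 792)/4096 = 2510/4096 = 0.613
- P(X ≥ 6 | 0.25) = 0.054

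An arm with exactly 5 responses is promising but misses the 50% criterion. That has probability 792/4096 = 0.193 at a true ORR of 50%, and 0.1576 − 0.0544 = 0.103 at 25%. The alternative route through median PFS can only raise 0.613 and 0.054; the plan gives no combined figure.

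**3. One data set under each sentence.** Take 7/12 responses (58.3%), acceptable safety and no immune change, with PFS assumed promising so that only the immune item is open.

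| Source | Result |
|---|---|
| Section 2.1, sufficiency sentence | Recommended |
| Section 8.0, one-arm rule | Considered for further study |
| Section 8.0, end of expansion paragraph, read as a requirement | Not recommended |
| Section 2.1, comparative sentence, read as a requirement | Not recommended |

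**4. What the rebiopsy measures.** Sections 4.3.3.2.1, 6.0 (footnote 9) and 7.1.2.7 place it at about day 11 to 13 of cycle 1. Section 5.2 adds the second drug at day 1 of cycle 2 in both arms. On that schedule the biopsy reflects trametinib alone in Arm A and pembrolizumab alone in Arm B. The later biopsy, at progression, is optional. Footnote 8 of the Study Calendar describes a different, three-cohort schedule; it and Section 5.2 must be reconciled, and this step rests on Section 5.2.

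**5. Illustration if the immune condition binds.** Let q be the probability that an arm with a true ORR of 50% shows a favourable change. The documents give no value for q. Under independence the joint probability is 0.806 × q. With no assumption about dependence, it lies between max(0, 0.806 + q − 1) and min(0.806, q).

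| q (assumed) | Independence | Bounds |
|---|---|---|
| 0.5 | 0.403 | 0.306 to 0.500 |
| 0.7 | 0.564 | 0.506 to 0.700 |
| 0.8 | 0.645 | 0.606 to 0.800 |
| 0.9 | 0.726 | 0.706 to 0.806 |

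**The case against.** The sentence in Section 2.1 is comparative, so it can be read as choosing between arms. It stands between a ranking that puts immune data second and a sufficiency statement with no immune condition. In Section 8.0, a combination may simply list inputs to a judgement. The decision paragraphs set out what happens when one arm or both arms pass, and leave the last word to the investigators. The correlates are declared exploratory, with unadjusted p-values. Section 4.3.1, after noting the disagreement on direction, still concludes that the evidence on balance favours an immune benefit from MEK inhibition. The trial is phase Ib with a safety primary objective.

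Much of this stands. Section 2.1 alone does not establish a conflict, and three stronger inferences fail:

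- **That the 80% power is wrong, or fits only one reading of the recommendation.** It is correct for the 5/12 rule and is presented as such. It does not describe the supplementary reading either, since that reading uses ORR of at least 50%, with a PFS alternative.
- **That Section 2.1 requires one arm to lead on all four criteria, so usually nothing is selected.** The sufficiency sentence that follows overrides so literal a reading, and Section 8.0 provides for comparable arms.
- **That a single directional marker, such as CD8+ density, must be fixed.** The exploratory objective names PD-L1. The supporting CD8+ material in Section 4 is prognostic correlation and a mouse comparison of the combination with anti-PD-1 alone, whereas the rebiopsy samples the lead-in.

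What the objection does not remove is the closing sentence of the expansion paragraph. Leaving the decision to judgement does not say which written criterion that judgement is to apply.

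**Conclusion.** The conflict is real and is anchored in Section 8.0. Its expansion paragraph joins immune change to efficacy as the basis for recommending a sequence; its later paragraphs, and the sufficiency sentence of Section 2.1, do not. If the joined wording is a requirement, an arm with 7/12 responses, acceptable safety and no immune change gets opposite answers. On the Section 5.2 schedule, the cycle 1 rebiopsy precedes the combination and is a poor gate for recommending it.

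The firm numbers are 0.806 and 0.158 for at least 5/12 responses, against 0.613 and 0.054 for at least 6/12; the second pair assumes that ORR of at least 50% means the observed rate and ignores the PFS route. The range 0.40 to 0.73 for a binding immune condition is not a finding about this trial. It assumes q of 0.5 to 0.9 and independence, whereas the trial's rationale links immune change to response; the bounds at q = 0.8 reach 0.800, so there may be almost no loss.

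This is a wording conflict that should be settled before expansion results are seen. It is not an error in the power calculation.

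**What to change.** - Reword the comparative sentence of Section 2.1 and the closing sentence of the expansion paragraph in Section 8.0 to state one rule: *a sequence is recommended if it meets the safety and efficacy criteria; immune and genomic findings are supplementary and are used only to help choose between two passing arms with comparable results.* This follows the decision paragraphs already in Section 8.0.
- Check the sentence in Section 8.0 that lists immune endpoints alongside ORR and toxicity, so that it fits the same rule.
- State that the 80% power and 0.16 alpha belong to the rule of at least 5/12 responses alone.
- Reconcile that rule with ORR of at least 50%: use one threshold throughout or explain why two are needed, and give the operating characteristics of the rule adopted, including the median PFS route.

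No new data or assays are needed. The work is two reworded sentences, a consistency check, and a short calculation once the efficacy rule is settled. The price is less freedom to cite immune markers when recommending an arm.

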2.2 Trial Diagram

Intercalated Trametinib and Pembrolizumab in Advanced KRAS Mutant NSCLC

^{*} Dose escalation in Arm A and Arm B followed by dose expansion (see 8.0 Statistical Analysis Plan). Trametinib starting 10 days on and 11 days off. Starting dose level 1.5 mg daily. Paired biopsy baseline, D11, and at progression (optional). Pt=platinum, PD=progressive disease, MTD=maximum tolerated dose, NSCLC=non-small cell lung cancer

3.0 OBJECTIVES & HYPOTHESES

3.1 Primary Objective & Hypotheses

Objective: To evaluate the safety and tolerability of pembrolizumab (MK-3475) when given in combination with trametinib in the proposed sequencing schemes in patients with advanced or metastatic non-small cell lung cancer with KRAS mutations.

Hypothesis: We hypothesize that pembrolizumab in combination with trametinib given with our lead in and intermittent sequencing schemes will be safe and tolerable.

3.2 Secondary Objective & Hypotheses

Objective: To assess in a preliminary manner the clinical efficacy of these combinations with the proposed sequencing schemes outlined above including overall response rate and progression free survival.

Hypothesis for Secondary Objective: We hypothesize that the combination of trametinib and pembrolizumab will be efficacious.

3.3 Exploratory Objective

Objective: To determine in an exploratory manner changes in PD-L1 expression as well as other immune correlates induced by MEK inhibition.

Hypothesis for Exploratory Objective: We hypothesize that lead in trametinib will demonstrate the most promise for preliminary efficacy based on clinical outcome and changes in immune micro-environment.

